**NOTE TO THE MEDWATCH REPORT AUTHOR:**

A *cover page* should accompany the *MedWatch* form indicating the following:

- “Notification from an Investigator Sponsored Study”
- The investigator’s name and address
- The trial name/title and AstraZeneca ISS reference number (ESR 17-13131)

\* **Investigator (sponsor)** must also indicate, either in the SAE report or the cover page, the *causality* of events *in relation to all study medications* and if the SAE is *related to disease progression*, as determined by the principal investigator.

All SAEs should be reported via confirmed facsimile (fax) transmission, or scanned and reported via electronic mail with a cover sheet to:

**SAE Email Address:** [contact]  
**SAE [contact]

If a non-serious AE becomes serious, this and other relevant follow-up information must also be provided to AstraZeneca and the FDA.

SAEs will be reported on MedWatch Form 3500A, which can be accessed at <http://www.accessdata.fda.gov/scripts/medwatch/>.

**MedWatch SAE forms should be sent to the FDA at:**

MEDWATCH  
[name]  
[name]  
Fax: [name] ([name])  
<http://www.accessdata.fda.gov/scripts/medwatch/>

If an ongoing SAE changes in its intensity or relationship to study drug or if new information becomes available, a follow-up SAE report should be sent within 24 hours to TCS using the same procedure used for transmitting the initial SAE report. All SAEs should be followed to resolution or stabilization.

**DSMB**

There will be no DSMB for this study.

**Dissemination of Safety Information from Astra Zeneca to Institution/Sponsor Investigator**

Astra Zeneca agrees to provide to the Sponsor Investigator SUSAR reports for the Study Product as they become available until all subjects in the Protocol have completed their last Study visit according to the Protocol (i.e. Last Subject Last Visit has occurred).

## 8 STUDY SCHEMATIC: TIME AND EVENTS

### X CHART

See Appendix C

### RESEARCH DESIGN AND METHODS

#### **Recruitment:**

A data search will be requested from MFA IT to generate a list of potentially eligible patients, and research staff will assess if patients meets basic eligibility requirements. Potentially eligible subjects may also be referred from the local clinics or providers. Phone numbers, (and potentially) home addresses will be obtained, in order to contact subjects about the research study, and see if they would be interested in participating. This contact will be done by calling subjects with an IRB approved phone recruitment script. When calling the subject for recruitment, a voicemail will not be left. When speaking to the subject over the phone a two-step verification process will be utilized, with subject's full name and date of birth to validate the person who picked up the phone is in fact the intended subject. Alternatively, subjects will be approached by the research staff in the MFA clinics, during a regularly scheduled visit with their provider. Any subjects who are interested will be asked a series of pre-screening questions either in person or over the phone to see if it is suitable to schedule a screening visit.

Alternative methods (all IRB Approved) for recruitment include: Study recruitment flyers posted in the MFA buildings, and in local clinics in the DMV area. Newspapers Ad will be placed in the Washington Post. The study recruitment flyer may be given to potentially eligible patients during their visit. Electronic bulletin board advertisement in the MFA clinics.

We will attempt to recruit patients from across all genders, races and ethnicities as much as possible to minimize these factors affecting results.

#### **Study Design Overview:**

We propose a 3-arm randomized, double-blind, placebo-controlled, parallel group, longitudinal study of 16-weeks duration. (See study design below), recruited over 20 months. Patients will be randomized to one of 3 groups:

Group A: **Dapa (10 mg)** + matched placebo for Saxa, Enroll n=15, retain n=10

Group B: **Dapa (10) + Saxa (5mg)**, Enroll n=15, retain n=10

Group C: matched **placebo** for Dapa + matched **placebo** for Saxa, Enroll n=15, retain n=10

This proposed study is based on patients with type 2 diabetes and VD, who are taking metformin and/or insulin for anti-diabetic treatment (See section 5 for full inclusion/exclusion criteria).

Though our study is over 16 weeks, we do not anticipate significant drop in HbA1C in between the three groups in this relatively short time period to act as a confounding factor on CD34+ cell number, function and gene expression.

Subjects will be taking 10 mg of Dapa, Dapa+Saxa combo (10 mg Dapa and 5 mg Saxa), or placebo. Dose titration of metformin, will not be allowed. Dose titration of insulin will be allowed to avoid hypoglycemia while maintaining HbA1C under 10%, preferably below 7% as that is the treatment guideline as per ADA. If the subject is only on metformin, Insulin will be started if the patient's glycemic control warrants it, as it can be titrated while the patient is on the study medications.

Visits 1, 2, and 3 with outcome measurements will be scheduled for the morning while overnight fasting (except water) to reduce diurnal variability, and clinical parameters will be obtained at scheduled office visits as depicted in the study schema and will be measured at each outcome visit as follows:

**Before Week -2 (Pre-screening):** Subjects will be pre-screened in person or over the phone to determine initial eligibility. If the pre-screening indicates possible eligibility, then the subjects will come to an in-person screening visit when next available.

**Week -2 (In-person screening):** Subjects will be screened and eligibility will be verified based on physical and laboratory tests. Equal numbers of male and female patients will be recruited.

**Week 0 (Visit 1):** At this stage patients will be randomized into the study. Subjects will have the first set of measurements. We will make sure that patients still meet the inclusion criteria. They will be started on one of the three study arms.

**Weeks 0, 8 and 16 (Visits 1-3):** Subjects will all have the same measurements and will continue on study medication or placebo. All primary and secondary measures as outlined before will be carried out.

### **Outcomes (For full outcomes please see section 2)**

#### **Primary Outcome: Cellular Biomarker of Endothelium**

The primary objective is to ascertain if 16 weeks of Dapa or Dapa+Saxa Combo therapy will improve CD34+ cell number, function and gene expression in type 2 diabetes with CVD.

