As mentioned before, we just finished a study using Saxagliptin in middle aged diabetic subjects and we are currently studying the role of Linagliptin, a dipeptidyl peptidase-4 (DPP4) inhibitor, on CD34+ cell number and function (IIS-Study) in a diabetic-CKD population. DPP4 is an enzyme that degrades not only GLP1 and GIP but also degrades a prime ischemic tissue chemotactic factor such as SDF1 alpha. The stem-cell “homing process” is based on the ability of DPP4 inhibitors to inhibit the degradation of SDF-1 and of its receptor CXCR-4, a pathway of importance for progenitor cell recruitment to ischemic tissue (myocardial or otherwise). Our study confirms that Saxagliptin will improve stem cell function particularly migration and “homing-in” of EPCs to damaged endothelial lining in type 2 diabetes subjects.

As mentioned before the presumed pathways of how Saxagliptin and Dapagliflozin would impact CD34 + cells are different. The former should improve migration and the latter should improve the progenitor stem cell itself by preventing increased intracellular glucose accumulation.

Both Dapa and Saxa are glucose lowering medications and glucose lowering per se can also improve EPC health as shown before. Clinically, this is best studied in a context of type 1 diabetes, where hyperglycemia is the principal agent that can influence cellular apoptosis. In these quoted studies, the glucose lowering effect that showed discernable EPC improvement was in the range of 3-4% of HbA1C. This is way more than what is afforded by Dapagliflozin, or Saxa or combination, which is a reduction of 0.8-1.2% in HbA1C or approximately 30mg/dl of glucose.

In our laboratory, in-vitro, we have shown EPC health to be affect when glucose levels increase to 360mg/dl from 100mg/dl with some cellular deleterious effect noted at 200mg/dl which is more pronounced at 360mg/dl.

We believe Dapagliflozin’s positive effect on progenitor cells may be more than simply a reduction in serum glucose values, similar to the effect seen by exercise intervention effect on CD34+ cells from prediabetes subjects in our human in-vivo experiments.

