## 2 RESEARCH HYPOTHESIS

We hypothesize that Dapagliflozin will improve EPC number and function AND Saxagliptin in addition to Dapagliflozin may have an additive effect to improve EPC number and function even more than Dapa alone, compared to placebo.

In this proposal we plan to conduct a placebo matched study with type 2 diabetes subjects on any doses of metformin, Insulin, Sulfonylureas ( including other insulin secretagogue like

meglitinides) or any combination above and has no history of DPP4 inhibitor, incretin mimetic or SGLT2 inhibitor intake history. Subjects will have known macrovascular complications (such as CVD, CVA, and PVD).

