### 3 STUDY OBJECTIVES

#### **PRIMARY OBJECTIVE: CELLULAR BIOMARKER OF ENDOTHELIUM**

The primary objective is to ascertain if 16 weeks of Dapa or Dapa+Saxa Combo therapy will improve :

CD34+ cell number,  
CD34+ migratory function and  
CD34+ gene expression in type 2 diabetes with CVD.

*Please see appendix A for the primary objective laboratory protocol.*

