## **9 STATISTICAL & DATA ANALYSIS**

### **STATISTICAL ANALYSIS**

Sandri et al. (2005, Study A, patients with peripheral arterial occlusive disease) found that in the control group, CD34+ cells increased from 372 cells per mL blood at baseline (SD 156) to 402 (SD 183) at 4 weeks. In their exercise training group, the increase was from 458 (SD 252) at baseline to 2977 (SD 852) at 4-weeks. We created a simulated data set with these parameters in order to calculate the percent of CD34+ cell variation that was explained by the group x time interaction. We tested two random effects mixed models, one without and the other with, a group x time interaction (group is treatment vs control; time is pre vs. 4-weeks post). The percent variance explained =  $(V_{no-int} - V_{int})/V_{no-int}$ , where  $V_{no-int}$  is the residual covariance parameter estimate without a group x time interaction term in the model, and  $V_{int}$  is the residual covariance parameter estimate with a group x time interaction term in the model. We found that based on the baseline and 4-week mean and standard deviation of CD34+ cell concentrations reported by Sandri et al., the interaction explained 84.5% of the variance in CD34+ cell concentration (a very large effect size). The correlation among repeated measures was  $r=.62$ . Using these parameters in G-Power3 (version 3.1.3), with 2 groups measured at 2 time points, in order to achieve power  $>.95$  would require a total sample size of 6 subjects (3 per group) each measured at 2 time points. If the group x time interaction explained only 50% of the variance in CD34+ cell count (still a large effect), we would need sample size of 8 (4 per group) in order to achieve power  $>.95$ , if only two groups are present.

In another study, Sen et al., in a sample of patients with pre-diabetes (n=11), CD34+ cell number increased from 0.8 (SEM 0.1) before exercise, to 1.4 (SEM 0.2) after exercise, a pre-post effect size (Cohen's d) of 1.81.

Taking multiple study observation factors, in order to detect an effect of this size using a 2-tailed paired t-test, with alpha=.05, for power  $>.95$ , the number of subjects required would be 7-8, per group.

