### **DATA ANALYSIS**

We will use generalized estimating equations (GEE) with robust standard error estimates to model within-subject and between-group differences over time. First we will investigate whether an unstructured correlation matrix is best fitting for the error term based on examination of the working correlation matrix output. If an exchangeable structure fits the data, we will consider using a random-effects mixed model with restricted maximum likelihood, due to its weaker assumption for missing data on the response variable. Using either approach, of primary interest will be the group (drug treatment) by time interaction, which will tell us whether the change in the dependent variable over time differs between groups. We will include as covariates any pre-treatment variables (e.g., demographics, baseline levels of the dependent variable, comorbidities, laboratory test values) that differ between groups even at a trend level of significance ( $p < .10$ ).

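### Three unranked primary domains have no success rule, and the three-arm interaction named as the primary test cannot show that the combination beats dapagliflozin alone

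*Combined protocol and SAP*

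**What the plan says.** The synopsis, Section 3 and Section 8 all make CD34+ number, function and gene expression primary together: "The primary objective is to ascertain if 16 weeks of Dapa or Dapa+Saxa Combo therapy will improve CD34+ cell number, function and gene expression". Section 3 narrows function to migration and then refers the reader onward: "Please see appendix A for the primary objective laboratory protocol". Appendix A is a laboratory protocol. It lists five migration conditions and 18 genes (4 + 5 + 4 + 2 + 3) and ranks none of them.

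The Section 2 hypothesis has two parts. Dapagliflozin should improve the cells compared with placebo, and "Saxagliptin in addition to Dapagliflozin may have an additive effect to improve EPC number and function even more than Dapa alone". Section 1 (Preliminary Results) expects the two drugs, saxagliptin and dapagliflozin in that order, to act differently: "The former should improve migration and the latter should improve the progenitor stem cell itself".

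The analysis text in Section 9 begins: "We will use generalized estimating equations (GEE) with robust standard error estimates". A mixed model is allowed as an alternative. Under either model, "of primary interest will be the group (drug treatment) by time interaction". Section 9 gives the purpose of this test in one clause: "which will tell us whether the change in the dependent variable over time differs between groups". The section gives no analysis alpha, primary time point, pairwise contrast, success rule across domains, multiplicity method or small-sample correction. Alpha .05 appears only in the sizing of a within-group paired t-test. The interaction sizing is "with 2 groups measured at 2 time points".

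**The concern.** Two questions are left open, and both affect what the trial may claim.

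The first is what counts as a positive trial. With three primary domains and no rule, the error rate depends on whether one domain, or all three, must succeed.

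The second is which test answers the second half of the hypothesis. A three-arm interaction asks whether any arm differs from any other over time. It can be significant because both active arms differ from placebo, with no difference between them. A report could then present a significant interaction as support for adding saxagliptin. The answer may also depend on the domain, since saxagliptin is expected to act through migration, and no domain is designated for this claim.

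A smaller question concerns the first-choice method. Robust standard errors are known to be too small with few subjects, and each arm is expected to retain only 10 to 12.

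**Working it through.** **Inputs.** Three arms; visits at weeks 0, 8 and 16 (Section 4). Retained per arm is 12 in the synopsis and 10 in Section 8, and Section 9 gives 36 in total but 10 per group. Both 12 and 10 are used. Effect sizes (in SDs of the week-16 change) and correlations are assumptions, because the documents give none for these drugs in this population.

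**The plan's own figures.** The pre-post effect size reproduces: SD = 0.1 × √11 = 0.332, and (1.4 − 0.8)/0.332 = 1.81. A two-sided paired t-test at .05 then has power .938 at n = 6, .976 at n = 7 and .991 at n = 8, which agrees with the stated 7-8. For the two-group interaction, a noncentral-F calculation with r = .62 gives totals of 4 (power .997) and 6 (.983), against the stated 6 and 8, so each is within two patients. None of these calculations covers three arms or combination versus dapagliflozin.

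**Error across three domains, no true effect, each tested at .05.**
- Any one counts, independent domains: 1 − .95³ = .143.
- Any one counts, simulated 2-df tests (100,000 trials): .142, .129, .113 and .085 at correlation 0, .5, .7 and .9.
- All three must succeed: at most .021 when no domain has an effect. It cannot exceed .05 under any pattern, since the test of any truly null domain must also reject.

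**Interaction when the combination adds nothing.** Take arm means 0, d, d for placebo, dapagliflozin and combination. The noncentrality of the 2-df week-16 test is λ = n Σ(μᵢ − μ̄)² = n(2d²/9 + 4d²/9) = 2nd²/3, with 3(n − 1) error df. For n = 12 and d = 1.2, λ = 2 × 12 × 1.44/3 = 11.52.

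| d (SD) | 12 per arm: λ | rejects | 10 per arm: λ | rejects |
|---|---|---|---|---|
| 0.6 | 2.88 | 29% | 2.40 | 24% |
| 0.8 | 5.12 | 48% | 4.27 | 40% |
| 1.2 | 11.52 | 84% | 9.60 | 75% |

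A combination-dapagliflozin contrast has true value zero in every row and rejects 5%.

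**Robust GEE on one endpoint, no true effect.** Simulation of 40,000 complete-data trials with three visits and within-subject correlation .6, using an uncorrected sandwich and chi-square reference. The 2-df week-16 test rejects 9.2% (12 per arm) or 10.3% (10 per arm). The 4-df interaction, with time categorical, rejects 13.6% or 15.6%. A Mancl-DeRouen corrected sandwich with t/F reference brings the 2-df test to 4.8-4.9%.

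**The case against.** The strongest reply is that the domains are joined by *and*. Read literally, all three must improve, and the error is then at most 5%. This stands to the extent that the error rate cannot be called uncontrolled. But the plan never states the all-three rule, so the rate is unspecified.

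Secondly, any model with a group-by-time term lets combination versus dapagliflozin be estimated. That is true. What is missing is its prespecification as the test of the claim, not the ability to compute it.

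Thirdly, Section 6 has data locked before unblinding and the unmasked analysis made according to the plan. A reader might infer that domains or contrasts will be picked after the results are seen. The documents do not say so, and a rule could still be fixed in time. The same section does allow clinical outcomes to be unblinded before the cellular data are analysed, so the rule should precede any unblinding.

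Fourthly, Section 9 says the investigators' earlier saxagliptin study supports the sizing for function and gene expression. That concerns sample size. It neither ranks the domains nor supplies a contrast.

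A reader might also count every migration condition and gene in Appendix A as a primary test and derive a much larger error rate. The documents do not support this: Appendix A is a laboratory protocol and does not make each item a primary test.

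Finally, the GEE inflation depends on how the robust errors are computed. The plan names neither a correction nor a reference distribution, so those figures are conditional.

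**Conclusion.** The concern holds in this form. The success rule is unspecified, which leaves the primary error anywhere from at most 5% (all three) to about 9-14% (any one, assumed correlation .9 to 0). The interaction is not evidence that the combination exceeds dapagliflozin alone. When the combination adds nothing, the interaction rejects 24-29% of the time at an assumed common effect of 0.6 SD and 75-84% at 1.2 SD. A reader might infer that it misleads most of the time, but that is true only for large common effects. If the robust GEE is run uncorrected with a chi-square reference, a single null endpoint is rejected about 9-10% of the time at week 16 and about 14-16% on the full interaction.

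The design can support an increment over dapagliflozin if the contrast is prespecified. With no saxagliptin-only arm, it cannot show additivity or synergy in the factorial sense.

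This should be corrected, but it does not make the data unusable.

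**What to change.** Amend Sections 3, 8 and 9 before any unblinding, including a partial one.

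1. **Contrasts.** Specify week-16 change contrasts from the model: dapagliflozin vs placebo, combination vs placebo, combination vs dapagliflozin. Base the claim of more than dapagliflozin alone only on the last, and name the endpoint.
2. **Small-sample inference.** Use the mixed model that Section 9 already allows, with t/F reference, or a Mancl-DeRouen corrected sandwich with t/F reference.
3. **Success rule.** Choose one measure per domain and state the rule. One option that keeps the stated objective is a 2-df week-16 test at .0167 in each domain, followed by that domain's three contrasts at .0167. If all arms are equal in a domain, nothing is claimed unless its 2-df test rejects (.0167). If they are not all equal, at most one pairwise null is true (.0167). The total is at most 3 × .0167 = .05. Naming number as the single primary, or requiring all three domains, would also control error. The choice is the sponsor's.
4. **The rest.** Treat the remaining migration conditions, CFU, flow panels and genes as exploratory.

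**Costs.** No new data are needed. For a 1.2 SD difference, a contrast at .0167 has at most 66% power (12 per arm) or 56% (10 per arm), against 81% or 74% at .05. Having to pass the 2-df test first lowers this further. The 2-df week-16 test replaces the full interaction as the decision test, and week 8 becomes supportive. Corrected standard errors widen intervals.

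Migration should not be made to wait for number without stating the price. In a sequence with number tested at .05, then migration and its contrasts at .025, power for combination vs dapagliflozin on migration (1.2 SD, between-endpoint correlation .5) falls from 81%/74% unadjusted (12/10 per arm). It becomes 57%/43%, 20%/15% or about 3% when number's effect in both active arms is 1.2, 0.6 or 0 SD.

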#### **Secondary Outcome: Arterial Stiffness and Renal Function, Non-Cellular Markers of Endothelium**

The secondary objective is to determine whether use of Dapa or Dapa+Saxa Combo alters markers of endothelial function such as: arterial stiffness, blood biochemical measures pertaining to endothelial, renal function, and urine exosomes.

#### **Tertiary Outcome: Metabolism Markers**

The tertiary objective is to determine whether use of Dapa or Dapa+Saxa Combo alters body composition, fasting lipid profile, and levels of insulin, glucose, and appetite controlling hormones.

## **PRIVACY PROTECTION**

All data collected for the research study will be collected under a random subject ID.

- All samples being sent to LabCorp for standard of care labs will be labeled with the subject ID, DOB, sex, Date of visit, time of collection, and Visit number. These samples will not be stored as they will be sent down to LabCorp immediately.
- All biological samples (blood + urine) being used for ELISA and CD34+ analysis will be labeled with the subject ID, Date of visit, and Visit number. No additional data will be provided with the samples. These samples be stored at either the MFA or GW, and will be analyzed The George Washington University Ross Hall in [name]

All de-identified study data will be stored electronically on RedCap. No PHI will be logged. All other patient files, including ICFs will be physically stored as patients files locked in the Department of Medicine in a member of the research staff's office. The only individuals who will have access to the study data will be the members of the research staff team, as indicated in the GW IRB Form "Research Team Personnel Form (HRP-201)".

